**GLOSSARY**

ADE	Adverse Device Effect
AE	Adverse Event
BMI	Body Mass Index
CFR	Code of Federal Regulations
Cm	Centimeter
CRF	Case Report Form
FDA	Food & Drug Administration
FU	Follow-up
GCP	Good Clinical Practice
ICF	Informed Consent Form
IEC	Institutional Ethics Committee
IRB	Institutional Review Board
Kg	Kilogram
Min	Minute
wk	Weeks
PI	Principal Investigator
USAE	Unanticipated, serious adverse event
USADE	Unanticipated, serious adverse device effect
SAE	Serious Adverse Event
Tx	Treatment
US	Ultrasound
USI	Ultrasound Imaging
W	Watt (Output Electric Power)

 Syneron Medical Ltd. Confidential	Clinical Study to Evaluate the Safety and Efficacy of the SlimShape Device for Abdominal Fat and Circumference Reduction			
	Protocol #	DHF22621	Rev. Date	October 8, 2017

**TABLE 1- STUDY SYNOPSIS**

Proprietary Name	SlimShape device
Design	
Prospective, one arm, baseline-controlled, clinical study for the evaluation of the SlimShape device for non-invasive abdominal fat and circumference reduction.
 
Study subjects will undergo SlimShape treatments on the abdominal area

Study Population	Up to 120 healthy adult volunteers, seeking for noninvasive abdominal fat and circumference reduction, male and females, 18 to 60 years of age from up to 10 investigational sites.
Treatment and Duration	
Eligible subjects will receive up to 3 bi-weekly treatments (2 weeks interval) with the SlimShape device utilizing the SlimShape Applicator Belt according to the study protocol.
 
The subject will return for 3 follow up visits: four weeks (4wk FU), eight weeks (8wk FU) and 12 weeks (12wk FU) after the last treatment.
 
Each subject will be enrolled for total expected study duration of up to 16 weeks.

Objective	The objective of this trial is to evaluate the safety and efficacy of the SlimShape device utilizing the SlimShape Applicator Belt for abdominal non-invasive fat and circumference reduction
Primary Objective	Statistically significant abdominal fat reduction post SlimShape treatments at 12 weeks follow-up (12wk FU) versus baseline
Primary Safety Objective	Evaluate the safety of the treatment with the SlimShape device utilizing the SlimShape Applicator Belt during all study
Secondary Objectives	
 
1. Statistically significant abdominal fat reduction post SlimShape treatments as measured by Ultrasound device at Pre Tx.3, 4 weeks, and 8 weeks follow-up (4wk FU and 8wk FU) versus baseline
 
2. Statistically significant abdominal fat reduction post SlimShape treatments as measured by calibrated Caliper device at Pre Tx.3, 4 weeks, 8 weeks and 12 weeks follow-up (4wk FU, 8wk FU and 12wk FU) versus baseline
 
3. Statistically significant abdominal circumference reduction post SlimShape treatment/s at Pre Tx.2, Pre Tx.3, 4 weeks, 8 weeks and 12 weeks follow-up (4wk FU, 8wk FU and 12wk FU) versus baseline
 
4. Investigator satisfaction: 
Satisfaction assessment will be performed by the study investigator using a pre-defined scale questionnaire. The investigator will answer this questionnaire at each follow-up visit (4wk FU, 8wk FU and 12wk FU)
 
 

Protocol #

DHF22621

Rev. Date

October 8, 2017

Page 7 of 39

## 5. Subject improvement and satisfaction:

Improvement and satisfaction assessment will be performed independently by the subject using a pre-defined scale questionnaire. The subjects will answer this questionnaire at each follow-up visit (4wk FU, 8wk FU and 12wk FU)

 Syneron Medical Ltd. Confidential	Clinical Study to Evaluate the Safety and Efficacy of the SlimShape Device for Abdominal Fat and Circumference Reduction			
	Protocol #	DHF22621	Rev. Date	October 8, 2017

Efficacy Endpoints	Primary and secondary objectives will be measured using the next efficacy endpoints: 
 
1. Fat thickness measurements using Ultrasound device
 
2. Fat thickness measurements using Caliper
 
3. Circumference measurements of the abdominal area using Measuring Tape
 
4. Investigator satisfaction using a pre-defined scale
 
5. Subject improvement and satisfaction using a pre-defined scale
 
6. Photography
 

Safety Endpoints	
 
1. The number, severity and type of any adverse event recorded throughout the study and post treatment (immediate and delayed response)
 

Statistical Methods	Descriptive statistics will be used to present changes in the assessments along the study course. Circumference measurements and subject assessments' and satisfaction data will be analyzed using two-tailed Wilcoxon Signed Rank test and/or paired t-test (alpha=0.05) to analyze the data difference from baseline and longitudinal change.

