### **Primary Objective**

Statistically significant abdominal fat reduction as measured by Ultrasound Imaging device post SlimShape treatments at 12 weeks follow-up (12wk FU) versus baseline.

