### **Primary and Secondary Efficacy Endpoint**

Primary and secondary objectives will be measured using the next efficacy endpoints:

1. Fat thickness measurements using Ultrasound device

 Syneron Medical Ltd. Confidential	Clinical Study to Evaluate the Safety and Efficacy of the SlimShape Device for Abdominal Fat and Circumference Reduction			
	Protocol #	DHF22621	Rev. Date	October 8, 2017

2. Fat thickness measurements using Calibrated Caliper device
3. Circumference measurements of the abdominal area using Measuring Tape
4. Investigator satisfaction using a pre-defined scale
5. Subject improvement and satisfaction using a pre-defined scale
6. Photography

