### Measure the Fat Thickness at the Treated Area – Ultrasound Imaging Device

Ultrasound Imaging (USI) provides a valid way for measuring fat thickness using known interfaces observed in any individual. USI relies on the ability to recognize different sub-skin interfaces and correctly identifying them, such as the **dermis** and the **subcutaneous fat layer** interfaces.

- Treated area is defined below the sternum and above the iliac. Mark the rectangle of the treated area with white pencil.
- Measure 2-4 cm from each edge of the umbilicus (superiorly and inferiorly) and 1.5-3 cm medially and laterally from the ends of these points (as **illustrated in Figure 5, white lines**). Make sure that the measurement points selected are at least 1 cm from the edges of the treatment area (including the width of the USI transducer, **see green arrows in Figure 5**).

UR – Upper Right measurement point, UL – Upper Left measurement point, LR – Lower Right measurement point, LL – Lower Left measurement point

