**Figure 5: Ultrasound Measurements Points**

[figure not shown]
- Mark the treated area and the measurements points on the transparency, to ensure measurement of the same point in each subsequent visit.

- d) Ultrasound measurements should be obtained from the edges of the measurement points, laterally (see **Figure 5 above, yellow dashed lines**).
- e) Place the applicator on the skin surface at angle of 90° (located the applicator under the measurement point line for consistency).
- f) Measurement should include all the area between the dermis and end of the fat tissue fascia. At least 2 measurements should be done in each measurement point.

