### **Follow-up Visit Measurements**

Follow-up measurements for weight, circumference and digital images will be used for comparative measurements with their respective measurement at baseline. Primary endpoints will be evaluated 12 weeks post last treatment. Secondary endpoints may be evaluated at all visits.

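### The primary ultrasound endpoint must be statistically significant, but no test is clearly assigned to it and no rule turns its four measurement points into one value per subject

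*Combined protocol and SAP*

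**What the plan says.** The Primary Objective section sets the criterion: "Statistically significant abdominal fat reduction as measured by Ultrasound Imaging device post SlimShape treatments at 12 weeks follow-up", compared with baseline. Instrument, time point and comparator are therefore fixed. The endpoint list adds only "Fat thickness measurements using Ultrasound device".

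The analysis text is short. The Statistical Methods row of Table 1 opens with "Descriptive statistics will be used to present changes in the assessments along the study course". It continues: "Circumference measurements and subject assessments' and satisfaction data will be analyzed using two-tailed Wilcoxon Signed Rank test and/or paired t-test (alpha=0.05". The stated purpose of those tests is the difference from baseline and the longitudinal change. In Data Analysis, under Follow-up Visit Measurements, the plan says "Follow-up measurements for weight, circumference and digital images will be used for comparative measurements with their respective measurement at baseline" and then "Primary endpoints will be evaluated 12 weeks post last treatment". The table of contents lists no other statistics section.

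The ultrasound section describes how the four points are located: "Measure 2-4 cm from each edge of the umbilicus (superiorly and inferiorly) and 1.5-3 cm medially and laterally from the ends of these points". They are labelled upper right, upper left, lower right and lower left (UR, UL, LR, LL). On replicates it says: "At least 2 measurements should be done in each measurement point".

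**The concern.** This is a one-arm, baseline-controlled study, so the within-subject ultrasound comparison carries the whole primary efficacy claim. Success is defined by significance, yet the plan does not clearly say which test supplies the p-value, or on what number per subject it is computed.

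If both stay open until the data are in, either can be settled with the results in view. A significant change at one favourable point and a significant change in the mean of all four could each be reported as the primary objective met. A later reader could not tell a prespecified result from a selected one.

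**Working it through.** **1. What the text assigns to ultrasound.** There is no stated calculation to reproduce: alpha 0.05 is simply given, and the figure of 120 subjects comes with no effect size, SD or power.

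| Place | Variables named | What it supplies |
|---|---|---|
| Primary Objective | Ultrasound fat thickness | Criterion 'significant', 12 weeks vs baseline; no test |
| Statistical Methods, first sentence | Assessments in general | Descriptive statistics |
| Statistical Methods, second sentence | Circumference, assessments of subjects, satisfaction | Two tests joined by 'and/or', two-tailed, 0.05 |
| Follow-up Visit Measurements | Weight, circumference, images | Comparison with baseline; no test |
| Follow-up Visit Measurements, next sentence | Primary endpoints | Timing only |

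Ultrasound is not named in any row that supplies a test.

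**2. Values per subject.** 4 points × at least 2 readings = at least 8 readings per subject per visit. A paired test needs one value per subject and visit. No section says whether to average, select or test the points separately.

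**3. Size if the point is open.** Assumptions: no true change, four equally correlated normal point-changes, and success if any point or the four-point mean is significant at two-sided 0.05. The correlation ρ is assumed. The SD of the mean relative to one point is √((1+3ρ)/4), which is 0.69, 0.79, 0.88 and 0.96 for the four values below. Results are from 400,000 simulated trials per row.

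| ρ | False reduction (nominal 2.5%) | Two-sided (nominal 5%) |
|---|---|---|
| 0.3 | 9.1% | 18.0% |
| 0.5 | 8.0% | 15.8% |
| 0.7 | 6.5% | 13.0% |
| 0.9 | 4.7% | 9.4% |

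The four-point mean on its own stays at about 5% two-sided. A subject-level version (n = 120, paired t-test, 40,000 trials) gives 9.1%, 7.7%, 6.6% and 4.4% for reductions. As an anchor, four independent points without the mean give 1 − 0.95⁴ = 18.5% two-sided and 1 − 0.975⁴ = 9.6% for reductions.

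**4. Size of 'and/or'.** n = 120, no true change, 200,000 trials per assumed distribution of changes, two-sided.

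| Changes | Either test significant | Both significant |
|---|---|---|
| Normal | 5.9% | 4.0% |
| Laplace | 6.6% | 3.2% |
| t, 3 df | 6.8% | 2.9% |

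Each test alone is close to 5% (paired t 4.7–4.9%, signed-rank 4.9–5.0%). As a check, P(either) + P(both) must equal the sum of the two single-test rates: 5.9 + 4.0 = 9.9, 6.6 + 3.2 = 9.8 and 6.8 + 2.9 = 9.7, all near 10. For reductions only, 'either' gives about 3.0–3.4% against 2.5%.

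**5. Satisfaction.** Table 2 measures satisfaction on the Table 6 scale and improvement on the Global Aesthetic Improvement (GAI) scale in Table 5. Return Visits has both rated on the GAI. Table 2 and Appendix I collect the questionnaires only at follow-up. The GAI is already a change rating with 0 for no change. The Table 6 scale is not, and it has no baseline value.

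**The case against.** The strongest reply is that the test sentence was meant to cover fat thickness. The sentence before it uses 'assessments' for study measures generally, Study Design Overview says fat reduction is assessed at each visit after baseline, and a difference from baseline suits fat thickness better than a questionnaire without one. That reading is arguable, so the documents do not show that the phrase means questionnaires only. Against it, circumference is also measured on subjects yet is listed separately, and Table 2 uses a very similar label for a questionnaire. Even if the reply is accepted, it supplies only a two-tailed alpha of 0.05. The choice between tests and the value to be tested remain open.

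A second reply concerns size, and it stands. A reader might infer that the trial runs at 9% to 18% error. The documents do not support that. The criterion is a reduction, so the directional figures are the relevant ones. No section permits success on a single point, and the objective speaks of one abdominal fat reduction. The correlations are assumed. The figures show what the open wording would allow, not what the sponsor plans.

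Third, the effect of 'and/or' alone is modest. That is also true.

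Fourth, a reader might infer that satisfaction can never be compared with baseline. That holds for the Table 6 scale but not if satisfaction is rated on the GAI, and the plan says both.

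**Conclusion.** The point holds and should be settled before any data are analysed. On the literal reading, the primary endpoint has a significance criterion with no test behind it. On the wider reading, the test is one of two and the per-subject value is undefined. Neither reading yields a reproducible primary analysis.

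The conclusion itself rests on the text alone. Its size rests on assumptions: equal between-point correlations of 0.3 to 0.9 and free choice among four points and their mean give about 9.1% to 4.7% false reductions instead of 2.5% (18% to 9% two-sided instead of 5%). The open choice of test is a smaller matter: 5.9–6.8% two-sided if either may count, 2.9–4.0% if both must. Under 'and/or' the stated 0.05 is not what is delivered.

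Three neighbouring items are separate and minor and add no weight here: the caliper visit lists in the synopsis and in Secondary Objectives differ at 12 weeks, no circumference height is named for testing, and the status of secondary p-values is not stated.

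**What to change.** In the Statistical Methods row and in Follow-up Visit Measurements, state that:

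- for each subject and visit, ultrasound readings are averaged within each point and then over UR, UL, LR and LL;
- the change in that value from baseline to 12 weeks is tested by one named two-sided test at 0.05 and reported with a 95% confidence interval. The paired t-test is one suitable choice, with the signed-rank test as sensitivity analysis only.

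The four-point mean and the paired t-test are not the only valid choices. What matters is that one of each is fixed in advance.

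Delete 'and/or' and name the same single test for circumference. Keep the longitudinal-change analysis, labelled as separate and secondary. Do not simply extend the sentence to the caliper: its section gives no measurement site or number of readings, so its per-subject value would have to be defined first.

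Reconcile Table 2 with Return Visits on which scale measures satisfaction. A GAI rating can be tested against 0. The Table 6 scale should be summarised at each follow-up visit without a baseline comparison.

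The cost is wording only, with no new data, visits or subjects. The downside for the sponsor is losing the choice of test and measurement point after the data are seen.

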## INTRODUCTION AND RATIONALE

### Background

Adipose tissue is a loose type of connective tissue specialized to store lipids. The majority of lipids stored in adipose cells are triglycerides formed from imported free fatty acids and glycerol. It is not uniformly distributed in the body. The major adipose depot is subcutaneous (about 80% of all body fat). In men it normally represents 15-20% of body weight and in women, 20-25% of body weight. A certain amount of body fat is necessary for normal female reproduction and health. Subcutaneous adipose tissue helps to shape, cushion and insulate the body and provides padding to some organs.

Liposuction is a procedure that can help sculpt the body by removing unwanted fat from specific areas. The increasing popularity of this procedure is associated with the evolution of techniques and equipment for fat removal, body reshaping and cellulite treatments. Besides the traditional suction-assisted lipoplasty, other options include ultrasound-assisted and external ultrasound-assisted liposuction, power-assisted liposuction, laser lipolysis as well as low-level laser-assisted liposculpture.

SYNERON CANDELA Syneron Medical Ltd. Confidential	Clinical Study to Evaluate the Safety and Efficacy of the SlimShape Device for Abdominal Fat and Circumference Reduction			
	Protocol #	DHF22621	Rev. Date	October 8, 2017

The efforts in the search for alternative non-invasive or minimally invasive techniques and new tools aim mainly at reducing downtime, and facilitating treatment for reduction of the localized fatty tissue areas.

The SlimShape device is a non-invasive, body contouring system based on radiofrequency (RF) and vacuum energies. The SlimShape provide a non-invasive approach to achieve a desired aesthetic effect (reduction in abdominal fat and circumference). The system is designed to enable an automatic, hands-free, full abdominal treatment that is based on a predefined user protocol. In addition, the system incorporates a skin-temperature control into the protocol, enabling accurate, stable and safer treatment.

## **Device Descriptions**

### **Syneron SlimShape Device**

The SlimShape system is comprised of two main parts:

- **The SlimShape console** which houses the system's computer, control panel, electronics, discomfort button, cooling system and other power and control devices which operate and control the system.
- **The SlimShape Applicator Belt** incorporates an array of vacuum cavities; each cavity includes a pair of RF electrodes and a suction pad. Each of the cavities moves independently of the others, applying software-controlled vacuum and RF pulses in turn.

### **Main Console**

The SlimShape console (Figure 1) incorporates the major modules required to deliver RF energy and negative air pressure (vacuum) to the applicator belt assembly, such as:

- RF generator
- Vacuum pump
- Computer
- 15" LCD control panel with touch-screen technology

[figure not shown]
SYNERON CANDELA Syneron Medical Ltd. Confidential	Clinical Study to Evaluate the Safety and Efficacy of the SlimShape Device for Abdominal Fat and Circumference Reduction			
	Protocol #	DHF22621	Rev. Date	October 8, 2017

**Figure 1: SlimShape System**

**The Applicator**

[figure not shown]
The *SlimShape applicator Belt* (Figure 2) incorporates a linear array of vacuum cavities; each cavity includes a pair of RF electrodes and a suction pad. Each cavity has sufficient mechanical degrees of freedom with respect to the neighboring ones, so that when the applicator belt is attached to the patient it conforms to the body curvature. The SlimShape applicator is tightened to the skin, ensuring vacuum tightness by a strap and buckle mechanism. An array of vacuum, air and RF valves/switches will distribute the RF and vacuum energies sequentially between the cavities according to a software-controlled routine. Each cavity has temperature sensors that enable accurate control of the skin's temperature.

**Figure 2: SlimShape Applicator**

SYNERON CANDELA Syneron Medical Ltd. Confidential	Clinical Study to Evaluate the Safety and Efficacy of the SlimShape Device for Abdominal Fat and Circumference Reduction			
	Protocol #	DHF22621	Rev. Date	October 8, 2017

A control button (Figure 3) is available to the patient in order to cease treatment if any discomfort is felt during the treatment. The discomfort button is designed to be held in the patient's hand during the entire treatment session. The patient should be instructed to press the button at any time he/she feels discomfort related to the treatment; this action stops the pulsing of vacuum and RF energy. The operator may then adjust the parameters or end the treatment session.

**Figure 3: Discomfort Button**

SlimShape is an upgraded version of the VelaShape device that is intended for abdominal fat reduction. The VelaShape device is cleared by the Food and Drug Administration (FDA). The upgraded version, the SlimShape device, is investigational and not yet FDA cleared.

**STUDY DESIGN OVERVIEW**

This study is a prospective, baseline controlled, multi-center, one arm clinical study showing the performance and safety of the SlimShape treatment for abdominal non-invasive fat and circumference reduction.

Up to 120 Healthy subjects in up to 10 investigational sites will be enrolled in this study. All subjects will undergo an assessment of their general health. During the treatment period, subject's fat thickness and circumference will be measured and up to three successive bi-weekly (two weeks interval) treatments will be performed.

The study subjects will undergo treatments with SlimShape device utilizing the SlimShape Applicator Belt.

During the follow-up period visit will be conducted as follow: 4 weeks (4wk FU), 8 weeks (8wk FU) and 12 weeks (12wk FU) post last treatment. Subject's fat thickness will be measured using 2 different methods (Calibrated Caliper and Ultrasound Imaging (USI)) and fat reduction will be assessed at each post baseline visit. Circumference will be measured in 3 measurements heights and circumference reduction will be assessed at each post baseline visit. Additionally, investigator and subject questionnaires will be completed. Finally, photography will be performed under visible light conditions of the front, right, left and back view. Most of the assessments will occur at each of the visits to the clinic.

 Syneron Medical Ltd. Confidential	Clinical Study to Evaluate the Safety and Efficacy of the SlimShape Device for Abdominal Fat and Circumference Reduction			
	Protocol #	DHF22621	Rev. Date	October 8, 2017

## **SUTDY OBJECTIVE**

The objective of this trial is to evaluate the safety and efficacy of the SlimShape device utilizing the SlimShape Applicator Belt for abdominal non-invasive fat and circumference reduction

### **Primary Objective**

Statistically significant abdominal fat reduction as measured by Ultrasound Imaging device post SlimShape treatments at 12 weeks follow-up (12wk FU) versus baseline.

### **Primary Safety Objective**

Evaluate the safety of the treatment with the SlimShape device utilizing the SlimShape Applicator Belt during all study.

### **Secondary Objectives**

1. Statistically significant abdominal fat reduction post SlimShape treatments as measured by USI device at Pre Tx.3, 4 weeks, and 8 weeks follow-up (4wk FU and 8wk FU) versus baseline.
2. Statistically significant abdominal fat reduction post SlimShape treatments as measured by Calibrated Caliper device at Pre Tx.3, 4 weeks, and 8 weeks follow-up (4wk FU and 8wk FU) versus baseline.
3. Statistically significant abdominal circumference reduction post SlimShape treatment/s at Pre Tx.2, Pre Tx.3, 4 weeks, 8 weeks and 12 weeks follow-up (4wk FU, 8wk FU and 12wk FU) versus baseline.
4. Investigator satisfaction:  
Satisfaction assessment will be performed by the study investigator using a pre-defined scale questionnaire. The investigator will answer this questionnaire at each follow-up visit (4wk FU, 8wk FU and 12wk FU).
5. Subject improvement and satisfaction:  
Improvement and satisfaction assessment will be performed independently by the subject using a pre-defined scale questionnaire. The subjects will answer this questionnaire at each follow-up visit (4wk FU, 8wk FU and 12wk FU).

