#### Marking height of circumference measurement

The abdominal circumference measurement will be marked at **1cm Above Iliac Height** (middle height of the treated area circumference). Patient should stand up straight when arms are placed at the rear of neck and head is positioned towards the horizon (Figure 7). Elbows will be positioned in front of the body (Figure 7).

The height for the circumference measurement will be marked at the anterior abdomen, at the back and at each lateral side of the body. Additional measurements will be taken at: **Waist Height** (upper height of the treated area circumference) and at **1.5inch (3.81cm) Below Navel Height** (lower height of the treated area circumference) See Figure 6 below.

SYNERON CANDELA Syneron Medical Ltd. Confidential	Clinical Study to Evaluate the Safety and Efficacy of the SlimShape Device for Abdominal Fat and Circumference Reduction			
	Protocol #	DHF22621	Rev. Date	October 8, 2017

*Figure 6: Circumference measurements points*

*Figure 7: Body positioning during marking height for circumference measurement*

The **1cm Above Iliac Height, Waist Height and 1.5inch (3.81cm) Below Navel Height** will be measured using the height measuring device (supplied by Syneron Medical). The marking pencil will be placed horizontally at the stage of the measurement device during the marking procedure. (Figure 7)

**Height of all measurements point will be recorded in the CRF** (will used as reference for the next visits measurements). As well, the **circumference results of each height** will be recorded at each visit.

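### Secondary objectives 1 to 3 are defined by statistical significance across 11 to 22 comparisons, with no test order, multiplicity control or success rule

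*Combined protocol and SAP*

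**What the plan says.** The Secondary Objectives section words objectives 1 to 3 as significant reductions from baseline at listed visits:

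- Objective 1, ultrasound: "as measured by USI device at Pre Tx.3, 4 weeks, and 8 weeks follow-up (4wk FU and 8wk FU) versus baseline".
- Objective 2, caliper: "as measured by Calibrated Caliper device at Pre Tx.3, 4 weeks, and 8 weeks follow-up (4wk FU and 8wk FU) versus baseline". The synopsis (Table 1) has a longer list: "as measured by calibrated Caliper device at Pre Tx.3, 4 weeks, 8 weeks and 12 weeks follow-up (4wk FU, 8wk FU and 12wk FU".
- Objective 3, circumference: "Statistically significant abdominal circumference reduction post SlimShape treatment/s at Pre Tx.2, Pre Tx.3, 4 weeks, 8 weeks and 12 weeks follow-up".

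Circumference is taken at three heights. The section on marking the height places the measurement at 1 cm above the iliac and describes the waist and below-navel heights as additional. The section on measuring circumference makes the same distinction. The CRF is to hold the "circumference results of each height" at every visit. No section says whether the heights are averaged, one is analysed, or each is tested.

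The only statement of a test and level is the Statistical Methods row of the synopsis: "Circumference measurements and subject assessments' and satisfaction data will be analyzed using two-tailed Wilcoxon Signed Rank test and/or paired t-test (alpha=0.05"). It does not mention ultrasound or caliper. Under Data Analysis, the paragraph on follow-up measurements adds "Secondary endpoints may be evaluated at all visits". Neither place gives a test order, an allocation of alpha, an adjustment, or a rule on how many comparisons must succeed.

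**The concern.** Because significance is the stated objective, these comparisons are not simply descriptive. Each significant result can be reported as an objective met, or partly met. Without an order or a success rule, the chance of at least one false claim grows with the number of tests. The visit, the circumference height and the test (Wilcoxon and/or paired t) could also be settled after the data are seen.

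This matters most for circumference. It is in the study title and the overall objective, yet only secondary comparisons support it. The primary ultrasound comparison at 12 weeks is not affected by this point.

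**Working it through.** The plan states no familywise error rate, so there is no figure to reproduce. The check counts the comparisons and then computes the chance of a false claim.

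**Step 1: count.**

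- Secondary Objectives section, circumference as one measure: 3 ultrasound + 3 caliper + 5 circumference = 11.
- With the synopsis caliper list: 3 + 4 + 5 = 12.
- Secondary Objectives section, each height tested: 3 + 3 + (5 × 3) = 21.
- Synopsis caliper list, each height tested: 3 + 4 + 15 = 22.

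Subject improvement and satisfaction at three follow-up visits would add 2 × 3 = 6, giving 28. They are left out because objective 5 is not worded as a significance claim.

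**Step 2: error per test.** The objectives concern a reduction. A two-sided test at 0.05 gives a false reduction with probability 0.05 / 2 = 0.025. The 0.05 level is documented for circumference and is an assumption for ultrasound and caliper.

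**Step 3: independent tests, all nulls true, any one success counts.** P(at least one false reduction) = 1 − (1 − 0.025)^m.

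- m = 11: 1 − 0.975^11 = 0.243
- m = 12: 1 − 0.975^12 = 0.262
- m = 21: 1 − 0.975^21 = 0.412
- m = 22: 1 − 0.975^22 = 0.427

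**Step 4: correlated tests.** All comparisons use the same subjects, and repeated visits share a baseline, so positive correlation is expected. The documents give no correlations, so a range was assumed. Test statistics were simulated as z_i = √ρ·f + √(1 − ρ)·e_i, with f and e_i standard normal (400,000 draws). A false reduction was counted when the largest z_i exceeded 1.96.

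| Tests | Independent | ρ = 0.5 | ρ = 0.9 | ρ = 0.95 |
|---|---|---|---|---|
| 11 | 24.3% | 15.2% | 6.6% | 5.1% |
| 12 | 26.2% | 16.0% | 6.7% | 5.2% |
| 21 | 41.2% | 21.7% | 7.9% | 5.9% |
| 22 | 42.7% | 22.1% | 7.9% | 6.0% |

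A less uniform pattern was also run for 22 tests, with assumed correlations of 0.5 to 0.9 within a measure, 0.3 to 0.8 between heights and 0.1 to 0.5 between methods. It gave 14.5% to 32.5%.

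None of these figures includes the extra freedom from choosing between the two tests.

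**The case against.** The strongest reply has four parts.

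- **The count.** 22 is a constructed maximum. Its extra caliper test appears only in the synopsis, and its extra ten circumference tests rest on a recording instruction rather than an analysis rule. The protocol also treats 1 cm above the iliac as the main height. All of this stands: 11 or 12 is what the objectives name, and 21 or 22 is what they fail to rule out. It would be wrong to say that no main height is identified, although the text never designates that height for analysis.
- **The level.** A reader might infer that every comparison is set at 0.05. The level is attached only to circumference and subject questionnaire data. This also stands, but a missing test and level for ultrasound and caliper leaves those claims less specified, not better protected.
- **The success rule.** The visits are joined by "and", so each objective could require success at every listed visit, which would cause no inflation. That reading is possible. So is the reading that each visit is a separate claim, and the documents do not choose.
- **The size.** A reader might quote 1 − 0.95^22 = 68%. That figure assumes independence, which is implausible here, and counts false increases that nobody would claim as success. The reduction-only figures are the relevant ones.

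**Conclusion.** The point holds as a gap in pre-specification: significance is the objective for 11 to 22 comparisons, and nothing limits which of them may be claimed. The chance of at least one false reduction claim is about 24% to 43% under independence, 15% to 22% at a common correlation of 0.5, and 7% to 8% at 0.9. The lower figure in each pair is for 11 tests and the higher for 22.

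These figures assume that every null is true, that each test is run at two-sided 0.05, and that any single success counts. The correlations are assumptions.

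The documents do not support the stronger inference that a false secondary claim is always far more likely than 5%. With 11 tests at a correlation of 0.95 the figure is 5.1%, although that is still about twice the 2.5% of a single test (5.1 / 2.5 = 2.0). Nor do they support saying that 22 tests are defined, each at 0.05. The change is worth making because it is cheap and the circumference claim depends on it.

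**What to change.** Make these changes before any outcome data are seen:

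1. Name one test, at two-sided 0.05, for the primary ultrasound comparison at 12 weeks. The Statistical Methods row currently assigns it neither.
2. Reconcile the synopsis and the Secondary Objectives section on the 12-week caliper comparison.
3. Designate the 1 cm Above Iliac height, already the main one in the measurement sections, as the circumference measure for inference.
4. If the primary is significant, test a short fixed sequence with the same test and level, stopping at the first non-significant step. One possible order is circumference at 12 weeks, caliper at 12 weeks (if retained), ultrasound at 8 weeks, ultrasound at 4 weeks. The order is the sponsor's choice, provided it is fixed in advance.
5. Report the other heights and visits as estimates with 95% confidence intervals and no significance claim.
6. Reword objectives 1 to 3 to match.

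This holds the error rate across the primary and the sequence at 0.05. It needs no extra subjects, visits or measurements and takes nothing from the primary. It is more than an edit of wording, because step 1 requires the primary analysis to be specified. The downside is that once a step fails, all later secondary results are descriptive only.
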